Other key descriptive variables: Treatment utilization: We will assess participant past and current substance use and mental health treatment utilization at baseline and follow-up. We will also assess primary care and specialty medical care visits, both within and outside the VA. This will be done using a modified version of the Treatment Services Review (TSR).⁵⁴ Quality of life: The PROMIS Profile-29 will be used to assess the following: anxiety, depression, physical function, fatigue, sleep disturbance, ability to participate in social roles and activities, and pain interference.⁵⁵ Demographics and military background. At screening, we will assess participants' branch, deployment history, gender, age, educational background, employment, income, race, ethnicity, and marital and cohabitation status.

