5.6 Schedule of Assessments

Schedule of Assessments – One Arm Trial			
Measures	Screening	Baseline	Post-Intervention
Informed Consent - Verbal	X		
Eligibility Review	X		
Demographics and Military Background		X	
Oral Fluid Samples		X	X
NIH Toolbox Loneliness Scale		X	X
Timeline Follow Back (TLFB)		X	X
Revised UCLA Loneliness Scale		X	X
Duke Social Support Index (DSSI)		X	X
Treatment Services Review (TSR)		X	X
PROMIS-29		X	X

Inventory of Drug Use Consequences - InDUC-2		X	X
Interpersonal Needs Questionnaire-12		X	X
Exit Interview			X

Schedule of Assessments - Randomized Clinical Trial				
Measures	Screening	Baseline	Post-Intervention	30-day Follow-up
Informed Consent - Verbal	X			
Eligibility Review	X			
Demographics and Military Background		X		
NIH Toolbox Loneliness Scale		X	X	X
Timeline Follow Back (TLFB)		X	X	X
Revised UCLA Loneliness Scale		X	X	X
Duke Social Support Index		X	X	X
Treatment Services Review (TSR)		X	X	X
PROMIS-29		X	X	X
Inventory of Drug Use Consequences (InDUC-2)		X	X	X
Interpersonal Needs Questionnaire-12		X	X	X
Exit Interview			X	

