training to help them understand the importance of reducing the risk for participants and learning how to recognize and report any AE or SAE. SAEs may include: death, hospitalization due to worsening psychiatric symptoms or suicidal ideation, or all life threatening or disabling/incapacitating events among research participants. AEs may include, but are not limited to: physical injuries, worsened physical or mental health, or inadvertent disclosure of confidential research information.

If an SAE occurs, the PI will immediately contact the DSMB and IRB, followed by a written report in 24 hours. He will make a decision whether there is sufficient evidence to suspend data collection, allow for further IRB review, modify the protocol, or make other changes to reduce potential risk to participants. The study will resume based on agreement of the PI, the IRB chair, and the DSMB. In the event that an AE that is not an SAE is reported to the PI, the PI will discuss the event with the DSMB. Immediate evaluation will occur to determine if any extra steps can be taken to minimize the likelihood of that type of AE occurring again. If changes can be made, a report/amendment will be written and submitted to the DSMB and IRB.

As part of a standard practice, the PI will supervise the implementation of one audit within 4 months after study recruitment and one regularly per year afterwards of the materials collected and produced as part of the study at each site to ensure proper confidentiality and compliance with ethical principles, including confirmation of verbal consent, questionnaire data, and to make sure that the research staff are following established protocols. The PI will provide an annual summary report of all AEs to the IRB and the DSMB as part of the annual review. If no adverse events have occurred, the report will state, "No adverse events affecting human participants have occurred during this project year."

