Adverse Events (AE). AEs may include, but are not limited to: worsened physical or mental health, or inadvertent disclosure of confidential research information. Serious Adverse Events (SAE) may include: death, hospitalization due to worsening psychiatric symptoms or suicidal ideation, or all life threatening or disabling/incapacitating events among research participants. Per IRB regulations, SAEs, any event resulting in a deviation from the study protocol (e.g., emergency hospitalization to address suicidal behaviors) or death will be reported to the PI within 24 hours and to the IRB in 48 hours. This will be completed in order to assess significance and determine an appropriate response. AEs that involve temporary distress will be noted by interviewers and provided to the IRB in an annual report.

Confidentiality of Records. Numerous protections are in place to reduce the likelihood of loss of confidentiality. All research data will be kept in locked filing cabinets in secure areas, absent of identifying information, and coded by research number only. Files containing items with identifying information will also be kept in locked filing cabinets, but these will be separate from cabinets containing data from this study. All electronic files, including therapy notes, will be maintained on a secure study folder behind the VA firewall. Only approved study team personnel will be granted access to this data. All identifiable information will be stored in a separate folder behind the firewall from the de-identified study ID and data.

Potential Benefits of Research to Participants and Others. There may be direct and/or indirect benefits of study participation. Participants are receiving a brief intervention that

addresses a transdiagnostic factor that may reduce both loneliness and substance use. Because this intervention can be used for both participants who are not engaged in treatment and for participants who are engaged in treatment, it may augment current services. Dissemination of the findings from the study will contribute to the extant literature, provide data to guide implementation, and may contribute to reducing loneliness and substance use.

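### No systematic adverse-event enquiry is described and no rule turns scheduled answers into event records, so the annual no-events sentence can support only that none were reported or identified

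*Combined protocol and SAP*

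**What the plan says.** **How events come to light (section 6.0).** The Data Safety & Monitoring Plan has staff trained in "learning how to recognize and report any AE or SAE". The handling of non-serious events begins "In the event that an AE that is not an SAE is reported to the PI". The Adverse Events paragraph adds: "AEs that involve temporary distress will be noted by interviewers and provided to the IRB in an annual report". Under Protection Against Risk, the two suicide questions are put when the interviewer is concerned. The PI also undertakes to keep track of negative outcomes and incidents, with no method given for finding them.

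**What counts as an event (section 6.0).** AEs include a worsening of physical or mental health. SAEs include admission to hospital for worsening psychiatric symptoms or suicidal ideation.

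**What is collected from everyone (sections 5.5 and 5.6).** The modified TSR covers substance use and mental health treatment, and section 5.5 adds: "We will also assess primary care and specialty medical care visits, both within and outside the VA". PROMIS-29 covers anxiety, depression, physical function and pain interference, among other domains. InDUC-2 covers consequences of drug use. All three are scheduled at baseline and post-intervention, and again at 30 days in the randomised phase. Neither schedule has an adverse-event row.

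**What is reported (section 6.0).** The PI sends the IRB and the DSMB an annual summary of AEs. If there were none, it must read: "No adverse events affecting human participants have occurred during this project year". The DSMB also reviews risks and benefits by treatment condition, and the reports to it cover biases with respect to AEs. Section 5.7 contains no adverse-event analysis.

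**The concern.** The annual sentence is about occurrence. The procedures described can show only what somebody recognised, noted or reported. Followed as written, a participant could mention a psychiatric admission while completing the TSR at the post-treatment call, and the answer could stay in the outcome data without reaching the event log. The IRB and the DSMB would then read that nothing had occurred.

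The comparison between arms is also at stake. No uniform question is asked and no blinding of the people who notice events is described. The two therapies differ in content: CBT-L/SUD has two sessions of exposure and behavioural activation. What a therapist hears about, and what is judged worth reporting, could differ by arm for reasons unrelated to the true event rate. A by-arm safety review needs even ascertainment to be interpretable.

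**Working it through.** The plan states no adverse-event rate, capture rate or safety sample size, so there is no figure to reproduce. The finding rests on setting the text side by side.

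1. *Is there an enquiry?* Both schedules in 5.6 were read row by row: no AE or SAE row and no suicide-risk measure. Sections 5.1, 5.5, 5.7 and 6.0 give no standard AE question, form, recall period or interval.
2. *Is there another route?* Three scheduled instruments overlap with the AE definition. The TSR bears on admissions and other care, PROMIS-29 on worsened mental or physical health, and InDUC-2 on harm from use. No text says that anyone compares these answers with the event record. The audits in 6.0 cover confidentiality, ethical compliance, consent, questionnaire data and adherence to procedures; reconciliation of events is not mentioned.
3. *What can the PI know at year end?* Only that no event was reported or identified. The sentence claims more.

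**Illustration of size (assumed values).** Let n = 36 participants (section 4.0: 6 one-arm plus 30 randomised), p the true risk that a person has an event, and s the chance that such an event reaches the log. Persons are treated as independent.

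- P(at least one true event) = 1 − (1 − p)^n
- P(empty log) = (1 − ps)^n
- P(at least one true event, given an empty log) = 1 − [(1 − p)/(1 − ps)]^n

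For p = 0.10 and s = 0.5: 1 − 0.90^36 = 0.977; 0.95^36 = 0.158; 1 − (0.90/0.95)^36 = 0.857.

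| p | s | P(≥1 true event) | P(empty log) | P(≥1 true event, given empty log) |
|---|---|---|---|---|
| 0.05 | 1 | 0.842 | 0.158 | 0 |
| 0.05 | 0.5 | 0.842 | 0.402 | 0.61 |
| 0.05 | 0.25 | 0.842 | 0.636 | 0.75 |
| 0.10 | 1 | 0.977 | 0.023 | 0 |
| 0.10 | 0.5 | 0.977 | 0.158 | 0.86 |
| 0.10 | 0.25 | 0.977 | 0.402 | 0.94 |
| 0.20 | 1 | >0.999 | <0.001 | 0 |
| 0.20 | 0.5 | >0.999 | 0.023 | 0.99 |
| 0.20 | 0.25 | >0.999 | 0.158 | >0.99 |

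With full capture, an empty log and no events are the same thing, and the sentence is true whenever it is used. With incomplete capture, an empty log is a poor guide over this whole range. The calculation covers the whole study, whereas the sentence is written per project year, so it shows the mechanism and does not forecast any one report.

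**The case against.** **Capture is not purely passive.** A reader might infer that events are found only if staff notice them or participants volunteer them. The documents do not support that. PROMIS-29, the TSR and InDUC-2 put relevant questions to everyone. Section 5.7 provides session-by-session feedback and attempts exit interviews with people who withdraw. Section 6.0 has the PI tracking incidents, and it reassesses suicide risk at follow-up contacts for people below imminent risk at baseline. This objection stands against the word *only*. The gap itself remains: the stated purposes of the feedback and interviews are drop-out, adherence, treatment experience and reasons for leaving, and nothing connects the questionnaires to the event log.

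**A missing row is weak evidence.** The 5.6 tables are not exhaustive. They omit the M.I.N.I. and the modified AARS, and do not mark the NIH Toolbox scale at screening although it decides eligibility. This is fair, and the point would fall if an enquiry were described elsewhere. None is in the text available. The appended treatment manuals were not available, and nothing in the protocol says that they contain one.

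**The sentence is conditional.** A reader might infer that the protocol certifies any year without *reports*. Its condition is that no events have *occurred*. That is correct, but without an enquiry the PI has no way to establish the condition.

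**It is not a declaration of safety.** A reader might take the sentence for one. It is a statement about a count, and the DSMB is also told of events as they arise. Confidence limits for zero events (exact two-sided 95% upper limits: 9.7% for 36 participants, 11.6% for 30, 21.8% for 15) might seem to measure the problem. They do not, because they would be the same with perfect capture, and the annual report need not carry them.

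**Conclusion.** The point holds as a gap in ascertainment and linkage. No systematic enquiry is described or scheduled, questionnaire answers that could reveal events are not routed to the event record, and the prescribed sentence says more than the process can show. Uneven ascertainment between arms is possible; the documents do not show that it will happen.

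The size cannot be fixed from the documents. Under assumed risks of 5% to 20% per person and capture of a quarter to a half, an empty log over the whole study would have probability between 0.023 and 0.636, and would coexist with at least one true event in 61% or more of such cases. These figures depend on the assumed risk and capture, and on independence between participants.

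This is a modest but worthwhile improvement for a 36-person feasibility study with an independent DSMB. It should be made because the procedures are meant to inform a fully powered trial.

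**What to change.** 1. **Sections 5.6 and 6.0:** add one scripted open adverse-event question, identical in both arms, at existing contacts. The minimum is the post-treatment assessment in both phases and the 30-day assessment in the randomised phase; the weekly sessions are preferable as well. Show it as a row in both schedules.
2. **Section 5.7:** after each assessment, check TSR-reported treatment and visits, and worsening on PROMIS-29, against the AE/SAE log. Define beforehand what change on PROMIS-29 prompts the check, and say whether InDUC-2 answers are included.
3. **Section 5.7:** tabulate events by arm, with the number of participants asked.
4. **Section 6.0:** change the annual wording to *No adverse events were reported or identified*, followed by the number of participants asked.

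The cost is a short question at calls already planned and a cross-check of data already collected, so a little more staff time. The recorded event count will be higher, and the DSMB should be told beforehand that this reflects better ascertainment.
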